#### Exclusion Criteria:

1. Other causes of chronic liver disease (Hepatitis C, Cystic fibrosis, biliary atresia, and alpha 1 anti-trypsin deficiency,)
2. Enrollment in any other clinical trial involving an investigational agent (unless approved by the designated physicians on the multidisciplinary team)
- 3.. The parent or guardian or child unwilling to provide consent or assent
4. Patients with severe hemorrhagic disorders
5. Patients with severe liver disease not caused by prolonged PN and renal insufficiency
6. Patients with uncontrolled diabetes mellitus

## 5.0 Enrollment/Randomization

NICU attendings will screen their patients for infants who need prolonged parenteral nutrition (TPN) and have Parenteral Nutrition Associated Liver Disease. The attending physician will ask the family if they would like more information about the study. [name] will be notified of these infants, and assess if they are suitable candidates. [name] or the NICU research nurses will explain the study to the infant's parents / legal guardians and obtain informed consent in the NICU at Vanderbilt Children's Hospital.

Assessment of the effect of treatment will be based on a non-randomized, open-labeled, prospective study of intravenously administered Omegaven™ fat emulsion to determine safety and preliminary efficacy in the treatment of PN associated liver injury.

## 6.0 Study Procedures

### Omega-3 Fat Emulsion (Omegaven™)

Bottles containing 50mL or 100 mL of 10% Omegaven™ will be purchased from International Pharmacy of Hamburg, Germany or directly from the manufacturer. Approval is pending from the FDA to allow for billing of Omegaven. Omegaven™ is manufactured by Fresenius Kabi AG, Bad Homburg v.d.h, Germany. Omegaven™ is formulated as an emulsion from fish oils. See attached Product Information Sheet.

While inpatient, the emulsion for each patient will be provided in its original container for volumes more than 96 ml/day. Doses less than 96 ml/day will be repacked into syringes to allow for administration via syringe pump. If patients are to be discharged home on Omegaven™, all doses will be administered from the original manufacturer's container.

All study materials will be stored securely until the time of administration. The bottles will be stored at room temperature below 30° C (do not freeze). Damaged or suspect drug will be returned unused to Fresenius- Kabi. Containers should be shaken before use.

All supplies for the study will be accompanied by accountability and shipping documents and will be maintained by the Investigator. Information recorded on these accountability and shipping documents will include relevant dates, batch numbers, quantities received or dispensed, to whom dispensed, returned drug and drug lost or damaged. At the end of the study, all used and unused Omegaven™ will be accounted for. If expired, the remaining drug supplies will be destroyed.

## Details of Omegaven™ Administration

After baseline labs are obtained (Table 2 and 3), therapy with Omegaven™ will be initiated at the goal dose of 1 gram /kg/day and is infused over 12-24 hours. Omegaven™ will be infused intravenously through either a central or peripheral catheter alone or in conjunction with parenteral nutrition. If additional fat calories are needed, they will be provided via the enteral route.. The same standards of care provided to all patients receiving parenteral nutrition solution will be followed. Routine nutritional monitoring is described in Table 3.

Table 2: Suggested Schedule Safety Monitoring for Omegaven™ Therapy

(To be done baseline pre-Omegaven™ therapy and weekly until direct bilirubin <0.4 mg/dL)

Parameter	Baseline	Biweekly	Monthly
Essential Fatty Acid Profile	X		X
PT	X	X	
PTT	X	X	
INR	X	X	

Table 3: Suggested Monitoring Schedule for Omegaven™ Therapy  
(Amended December 26, 2006)

Parameter	Baseline (pre- Omegav- en)	Dail y	Q week * -	Periodicall y**
Weight	X	X		
Fluid balance	X	X		
Vital Signs	X	X		
Catheter site/function	X	X		
Laboratory test:				
Sodium	X		X	
Potassium	X		X	
Chloride	X		X	
Glucose	X		X	
BUN	X		X	
Creatinine	X		X	
Triglycerides	X		X	
Calcium	X		X	
Magnesium	X		X	
Phosphorus	X		X	
Prealbumin	X		X	
C reactive protein	X		X	
Albumin	X		X	
Total protein	X		X	
SGPT	X		X	
Alkaline phosphatase	X		X	
Bilirubin (total and direct)	X		X	

GGT	X		X	
AST	X		X	
Copper				X
Iron				X
Vitamins A,D,E				X
Essential Fatty Acid Profile	X		X	
Free cholesterol	X		X	
Free fatty acids	X		X	
Lipid Panel	X		X	
Hemoglobin	X		X	
Hematocrit	X		X	
RBC	X		X	
WBC	X		X	
Platelets	X		X	
PT	X		X	
PTT	X		X	
INR	X		X	
Fibrinogen				
Selenium				X
Zinc				X
Carnitine				X
Aluminum				X
Retinol binding protein (check when getting Vit A)				X

\* More often as necessitated by clinical course; may be reduced in patients who are stable and whose biochemical markers have improved. Refer to protocol for additional information

In the event that a patient is unable to achieve adequate calories parenterally and is unable to tolerate enteral feeds, it may be necessary to evaluate whether or not the patient should continue the study with Omegaven™ as monotherapy or resume therapy with conventional fat emulsions so that additional parenteral fat calories can be given. The clinical team, in conjunction with the patient's primary physician, will determine if the patient should be removed from the protocol. The DSMB will also be notified.

Prior to the administration of each Omegaven™ dose, two nurses will check the dose dispensed against the physician's orders and verify that the infusion pump settings (hourly rate, volume to be infused) are correct before the infusion is started.

As previously mentioned, Omegaven™ may be infused in the same manner as conventional fat emulsions through either a central or peripheral line. The emulsion is isotonic. It is compatible with parenteral nutrition solutions and may be co-infused via y-site. Omegaven™ may be infused through a 1.2micron inline filter.

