## 4.0 Inclusion/Exclusion Criteria

### Inclusion Criteria:

1. Patients aged 0 to 2 years will be PN dependent (unable to meet nutritional needs solely by enteral nutrition) and are expected to require PN for at least another 30 days
2. Patients considered eligible for study participation must have parenteral nutrition associated liver disease (PNALD) as defined as a direct bilirubin of >2.5 mg/dl or more. Other causes of liver disease should be excluded. A liver biopsy is not necessary for treatment.
3. Signed patient informed consent.

4. The patient must have utilized standard therapies to prevent the progression of his/her liver disease including surgical treatment, cyclic PN, avoiding overfeeding, reduction/removal of copper and manganese from PN, advancement of enteral feeding, and the use of ursodiol (i.e., Actigall®).

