#### Duration of Therapy

Patients will remain on Omegaven™ until weaned from PN. Patients may continue monotherapy with Omegaven™ as an additional source of calories after the dextrose/protein portion of PN is discontinued

In the event that a patient who has been listed for a liver or liver/intestinal transplant has an organ become available, the participation in this protocol will not preclude them from receiving the transplant.

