### ***Analysis of Efficacy of Omegaven™***

The primary outcome to gain preliminary evidence of efficacy will be based on the time from baseline to normalization of bilirubin level, i.e, first time point among three consecutive in which bilirubin is  $< 2\text{ mg/dL}$ . We do not anticipate that any subject will present a rebound on direct bilirubin after normalization. However, we will describe the cohort with respect to the frequency of rebounds in bilirubin levels.

Crude comparisons of time to normalize direct bilirubin levels using Omegaven™ Results of these analysis will be compared with results of analysis excluding subjects who die or are transplanted. Time to reach a total bilirubin of 1.2 will also be compared using survival analysis methods. Analysis of this outcome will proceed as described for direct bilirubin.

We will also describe individual profiles over time (i.e., 2 months before baseline or birth until end of follow-up period) for all subjects using graphical methods. Trends in liver function markers over time will be explored using generalized linear models in which correlations of observations within subjects will be accounted using a generalized equations or random effects approach. In these models we will hypothesize that for both groups biochemical levels increase for all tests with equal slope before treatment. After treatment, however, levels should be decreasing for patients in the Omegaven™ group. We will perform these analyses including only subjects who did not die or undergo transplantation and including all subjects but assigning for subjects who died or underwent a transplant their worse possible outcome after they died or had the transplant. Using descriptive statistics, we will also explore the association between spikes in blood tests over time and predictors including transfusions of red blood cell products and blood stream infections.

Assessment of efficacy will be also based on comparison of means (or medians) of the mean and maximum modified PELD scores of each subject across all follow-up weeks. Adjustments of these comparisons for potential confounders will be based on linear regression models. Mean rates of infection will be compared. Liver transplant, mortality, and red blood cell product transfusion events will be collected.

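### The primary efficacy endpoint needs three consecutive low bilirubin values, yet bilirubin testing may be thinned without a floor once an infant improves

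*Combined protocol and SAP*

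**What the plan says.** - **Endpoint.** Section 10.0, Analysis of Efficacy: "The primary outcome to gain preliminary evidence of efficacy will be based on the time from baseline to normalization of bilirubin level". Normalization is the "first time point among three consecutive in which bilirubin is" below 2 mg/dL. The rule counts values. It gives no spacing, no maximum gap, and no instruction for an infant who has one or two low values at last contact.
- **Testing.** Section 6.0, Table 3, is titled "Suggested Monitoring Schedule for Omegaven™ Therapy". Total and direct bilirubin are in the starred weekly column. The star leads to a footnote that allows more frequent testing if the clinical course calls for it. It also says that testing "may be reduced in patients who are stable and whose biochemical markers have improved". No lower limit is set and the endpoint is not mentioned.
- **Neighbouring text.** The Table 2 header reads, in part, "weekly until direct bilirubin <0.4 mg/dL". Table 2 itself lists only the fatty acid profile, PT, PTT and INR, in biweekly and monthly columns. Bilirubin is not a row.
- **Length of observation.** At entry, infants "are expected to require PN for at least another 30 days". Under Duration of Therapy, "Patients will remain on Omegaven™ until weaned from PN". Discontinuation of Therapy adds at least 2 months of follow-up after treatment stops, without a bilirubin schedule for that period.

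**The concern.** The condition that permits fewer tests is improvement in the biochemical markers, and improvement in bilirubin is what the endpoint measures. The infants most likely to reach the endpoint are therefore those whose testing may become sparse. This can act in two ways.

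1. **Confirmation.** If testing is thinned before the third low value, a true and lasting responder may have fewer than three values when observation ends.
2. **Dating.** A value can be improved and still be above 2. If thinning starts then, the first low value is found later and the event time is coarser. Dating the event to the first of the three values does not repair this. It does protect the event time of a confirmed responder whose testing was thinned only after the first low value.

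Both the number of events and their times would then partly reflect local decisions about test frequency.

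**Working it through.** The plan states no sample size, power or event count, so it has no figure to reproduce. The check is timing arithmetic and needs no model of how bilirubin falls.

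**Inputs from the documents.** Three consecutive values (Section 10.0); weekly listed interval, 7 days (Table 3); at least 2 months of follow-up after treatment, taken as 60 days (Section 6.0).

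**Assumptions.** The reduced interval d is not given, so 14, 28, 30 and 42 days are shown. The fall below 2 is sustained. Tests fall exactly on schedule, with no extra test at last contact. The fall occurs at a uniformly random point between two tests, so U is uniform on (0, 1).

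**Step 1: span of three values.** Span = 2 × d, which is 14 days at weekly testing, 28 at 2-weekly, 56 at 4-weekly, 60 at 30-day and 84 at 6-weekly.

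**Step 2: chance of non-confirmation.** Let W be the days from the true fall to the end of follow-up.

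- Weekly until the first low value, then every d days: unconfirmed if 7U + 2d > W.
- Already every d days before the fall: unconfirmed if dU + 2d > W.

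For W = 60 and d = 28:

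- Thinned after the first low value: 7U + 56 > 60, so U > 4/7 and the chance is 3/7 = 0.43.
- Thinned before the fall: 28U + 56 > 60, so U > 1/7 and the chance is 6/7 = 0.86.

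For d = 30 the span alone is 60, so the chance is 1 in both cases.

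Each cell gives thinned after the first low value / thinned before the fall:

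| W (days) | weekly | 14-day | 28-day | 30-day | 42-day |
|---|---|---|---|---|---|
| 30 | 0 | 0.71 / 0.86 | 1 / 1 | 1 / 1 | 1 / 1 |
| 45 | 0 | 0 / 0 | 1 / 1 | 1 / 1 | 1 / 1 |
| 60 | 0 | 0 / 0 | 0.43 / 0.86 | 1 / 1 | 1 / 1 |
| 75 | 0 | 0 / 0 | 0 / 0.32 | 0 / 0.50 | 1 / 1 |
| 90 | 0 | 0 / 0 | 0 / 0 | 0 / 0 | 0.14 / 0.86 |

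**Step 3: effect of the length of observation.** Here the day of the fall is assumed uniform over a range, and the chance is averaged over it.

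| Total follow-up; day of fall | weekly | 14-day | 28-day | 30-day |
|---|---|---|---|---|
| 120 days; day 14 to 90 | 0 | 0.02 / 0.07 | 0.39 / 0.53 | 0.44 / 0.59 |
| 180 days; day 14 to 120 | 0 | 0 / 0 | 0.01 / 0.10 | 0.03 / 0.14 |

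**Step 4: event date.** If testing is already at interval d when the fall occurs, the first low value comes on average d/2 after it. That is 3.5 days at weekly testing and 14 days at 28-day testing, a mean shift of 10.5 days.

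**Step 5: with weekly draws kept until confirmation.** Non-confirmation needs 7U + 14 > W, which cannot happen once W is 21 or more. Only falls in about the last 14 to 21 days of follow-up are missed.

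**The case against.** **The loss may be small.** This stands. Two-weekly testing loses nobody whose fall comes 45 or more days before follow-up ends, and long PN courses leave time even for monthly tests. The 2 months are a minimum, and no text mentions 4-weekly bilirubin testing. But no text rules it out either.

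**The Table 2 header suggests monitoring well past the endpoint.** It does point that way, since following a direct bilirubin down to 0.4 mg/dL would pass 2 first. But bilirubin is not in that table, the header disagrees with the table's own columns, and the Table 3 footnote says something else. The footnote refers to the protocol for more information, and the text contains none on this point. Appendix A, the procedure calendar, could not be checked.

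**Stronger readings that the documents do not support.**

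- *Observation ends when PN stops.* A reader might calculate larger losses on that basis. Follow-up continues for at least 2 months after treatment stops, in hospital or clinic.
- *Testing is thinned differently in treated infants and a soybean comparator.* Table 3 is a schedule for Omegaven, and nothing describes how comparator infants are tested.
- *The plan censors unconfirmed responders.* Section 10.0 has no censoring rule. It is silent on these infants.
- *The bias favours Omegaven.* Lost or late confirmation mainly understates its effect. Sparse testing can also miss a rebound between tests, so the net direction is uncertain.

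**Conclusion.** The concern holds as an internal mismatch: the endpoint needs repeated values, and the footnote lets those values become sparse because the infant has improved. The harm is material only if the reduced interval is about a month or longer and the fall comes late. At 60 days before the end of follow-up, the chance of missing a sustained responder is then 0.43 to 0.86 at 28-day testing and 1 at 30-day testing, against 0 at weekly or 2-weekly testing. These figures rest on assumed intervals, on 60 days for the 2 months, and on tests kept to schedule. The share of infants affected cannot be stated, because neither the reduced interval nor the total follow-up is given. This should be corrected, but it does not by itself invalidate the endpoint.

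**What to change.** - Reconcile the Table 3 footnote and the Table 2 header with Section 10.0. For endpoint ascertainment, keep the bilirubin draw at the weekly interval that Table 3 already lists until the third consecutive value below 2 mg/dL is recorded, including during post-treatment follow-up. Other tests may still be reduced.
- Add a sensitivity analysis to Section 10.0 in which infants with only one or two low values at last contact count as events at the first low value. Report how many there are.
- An interval-censored analysis is optional. With weekly draws the event is already located to within about 7 days, so it would add little.

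The cost is one footnote, a reconciled table header, one or two sentences in Section 10.0, and a few extra bilirubin draws in improving infants.

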#### Dose Modification

#### Lipid Intolerance

If lipid intolerance develops, defined as serum triglyceride levels > 200 mg/dL, the following will be considered prior to reducing the dose:

a) If the level was obtained while the patient was receiving a continuous 24- hour infusion of Omegaven™, the total dose should be infused over 20 hours, and a repeat serum triglyceride level obtained prior to resuming the infusion 4 hours later.

b) Other sources of lipid intolerance should be considered and addressed (drugs, renal disease)

If the triglycerides continue to remain high despite the aforementioned interventions, a dosage reduction of 25% of the current dose will be considered.

#### Duration of Therapy

Patients will remain on Omegaven™ until weaned from PN. Patients may continue monotherapy with Omegaven™ as an additional source of calories after the dextrose/protein portion of PN is discontinued

In the event that a patient who has been listed for a liver or liver/intestinal transplant has an organ become available, the participation in this protocol will not preclude them from receiving the transplant.

#### Disruption of Therapy

In event that Omegaven™ cannot be administered (i.e. loss of central venous catheter access, fluid restrictions, need to administer an incompatible medication/blood product), the infusion of Omegaven™ may be interrupted and resumed when the conflicting situation is resolved. Some potential interventions that can be used include:

Situation	Possible Solution
Loss of central venous access	Administer via peripheral route
Fluid restriction	Consult with pharmacy to concentrate PN, medications to allow for administration
Limited access, need to administer incompatible medications	Stop Omegaven™ infusion, flush catheter with either NS or dextrose, administer incompatible medication, flush catheter, resume infusion; may be necessary to infuse Omegaven™ over greater than 12 hours (use multiple syringes so as to keep maximum hang time of Omegaven™ source container less than 12 hours)

#### Discontinuation of Therapy

Patients will continue to be followed by the PI if in-patient or if discharged they will be followed in the Out-Patient GI Clinic upon discontinuation of therapy with Omegaven™ for a minimum of 2 months after the treatment is stopped.

#### Data Collection

All clinical and laboratory research data will be abstracted from source documents (medical records) and recorded and maintained on study specific case report forms (CRF). These CRFs will be stored within individual subject binders in accordance with Good Clinical Practice Standards and FDA requirements. Study materials will be kept in the Principal Investigator's locked office and access will be restricted to authorized study staff only. Subject confidentiality will be maintained by recording subject-specific data using a unique confidential study identifier.

## 7.0 Risks

## Potential Risk of Omegaven™ Treatment

Omegaven has been studied in animal pre-clinical models as well as Phase I, II, III, and post marketing human trials in both Europe and Asia. Prolonged bleeding time and an inhibited platelet aggregation can occur. It should not be administered to patients known to be allergic to fish or egg protein.

Contraindications to Omegaven™ include the following:

- Impaired lipid metabolism
- Severe hemorrhagic disorders
- Unstable diabetes mellitus
- Collapse and shock
- Stroke/Embolism
- Recent cardiac infarction
- Undefined coma status

Side effects:

The infusion of Omegaven™ can lead to a prolonged bleeding time and an inhibited platelet aggregation. In rare cases, patients may experience a fishy taste.

The administration of Omegaven™ should be stopped or reduced if there is a marked increased in blood glucose levels during the Omegaven™ infusion. Undesirable effects that are seen during the infusion of Omegaven™ that may also occur with conventional fat emulsions (i.e., Intralipid®) include:

- Slight rise in body temperature
- Heat sensation and/or cold sensation
- Chills
- Flushing or cyanosis
- Lack of appetite, nausea, vomiting
- Dyspnea
- Headache, pain in the chest, bone pain
- Priapism
- Increase/decrease blood pressure
- Anaphylactic reactions/erythema

A recent review of the literature suggests a slight change in risk status. There was a single case report of an infant developing anemia : [J Pediatr.](#) 2010 Feb;156(2):324-6.e1, Parenteral fish oil-associated burr cell anemia. [Mallah HS](#), [Brown MR](#), [Rossi TM](#), [Block RC](#). The mechanisms responsible for formation of burr cells are unknown but have been attributed to changes in composition of the lipids of the red blood cell membrane. These changes affect erythrocyte fragility and ultimately cause shape alterations, which make the red blood cells more susceptible to trapping and destruction by the spleen. None of the 13 infants in our study has developed any anemia and we will now monitor for that reported complication.

Other expected adverse events that are common to all patients with short bowel syndrome, regardless of the type of fat emulsion they receive, include blood stream infections and re-admittance to hospital. Causes for re-hospitalization include dehydration, bloodstream infections, electrolyte abnormalities, bowel obstruction, and central venous catheter malfunction.

Overdose:

In the event of an overdose of Omegaven,™ there is a risk of developing fat overload syndrome that may occur when the triglyceride level rises >200 mg/dL acutely as a result of too rapid a rate of infusion, or chronically at high infusion rates in associated with a change in the patient's clinical condition (e.g., renal

dysfunction, sepsis). In such cases, the infusion should be stopped or, if necessary, continued at a reduced dose. Metabolic acidosis has occurred in patients receiving Omegaven™ at excessive doses without simultaneous administration of dextrose.

#### Potential Benefit of Omegaven™ Treatment

Omegaven™ may be effective in stabilizing or reversing hepatic injury associated with the use of parenteral nutrition. It may allow the patient to continue to receive the majority of his/her caloric intake from parenteral nutrition while advancing on enteral nutrition or awaiting liver or liver/intestinal transplant

